AdventHealth Employees: Recruitment efforts will follow AdventHealth recruitment SOPs for research. AdventHealth Employees will not be individually targeted nor excluded from study participation based on employment. AdventHealth employees who engage the TRI asking to participate in the study will be processed per standard consent procedures for participants. In addition, during the consent process, the study staff will review standard consent language stating that an employee's participation or lack of participation in the study will not affect their employment status or relationship with AdventHealth.

Inclusion Criteria

1. Participant must be male or female, ages 60 through 80 years of age.
2. Participant has pre-diabetes or has been diagnosed with type 2 diabetes and taking 0-3 oral hypoglycemic agents, which include basal insulins, incretin mimetics, DPP-4 inhibitors, Sulfonylureas and/or Metformin therapy, and has an Hgb A1C < 9.0%.
 - a. Participants on Insulin, , SGLT2 inhibitors, and Thiazolidinediones will be excluded.
 - b. Pre-Diabetics are defined as having an HgbA1c of greater than or equal to 5.7% and less 6.5%, or a fasting glucose of greater than or equal to 100 mg/dl and less than 126 mg/dl or has a glucose of greater than or equal to 140 mg/dl and less than 200mg/dl at the 2 hour blood draw during OGTT
3. Participant must have renal function with an estimated glomerular filtration rate (eGFR) > 45 ml/min/1.73m² determined at screening.
4. Participant's triglyceride level is < 350 mg/dl and LDL cholesterol is ≤ 150 mg/dl at screening.
5. Participant states willingness to follow protocol as described, the prescribed activity level and completing any forms needed throughout the study.
6. Participant has voluntarily signed and dated an informed consent form, approved by an Institutional Review Board/Independent Ethics Committee, and provided Health Insurance Portability and Accountability Act authorization (HIPAA) or other privacy authorization prior to any participation in study.

Exclusion Criteria

1. Participant has type 1 Diabetes.
2. BMI > 40.0 kg/m²
3. Participant is actively pursuing weight loss and/or lifestyle changes.
4. Participant has a history of pressure ulcers.
5. Participant has a stated history of Deep Vein Thrombosis (DVT), pulmonary embolism, or a known hypercoagulable condition, or other clotting or bleeding disorders.
6. History of gastrointestinal or intracranial hemorrhage.

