⁹Resting Metabolic Rate/Respiratory Quotient (RMR/RQ): Indirect calorimetry will measure the resting metabolic rate/respiratory quotient (RMR/RQ) and substrate utilization after an 8-hour overnight fast using a MAX II Metabolic cart (AEI Technologies, Pittsburgh, PA). The analyzer will be calibrated before each subject with standardized gases containing 5% CO₂, 21% O₂ and balance N₂. Subjects will be instructed to lie in a Semi-Fowler's position and remain motionless and awake during these periods. A transparent plastic hood connected to the device will be placed over the head of the subject. Calculations of O₂ consumption (VO₂) and CO₂ production (VCO₂) will be made by comparing a single measure of the O₂ and CO₂ concentrations of the testing room to continuous measurements of O₂ and CO₂ concentrations in expired air diluted in a constant air flow (20-50 L/min) generated by a pump. From the above, energy expenditure standardized for temperature, pressure, and moisture will be calculated at one-minute intervals.

⁸Graded exercise testing: Volunteers must pass the medical screen before they will be allowed to undergo the exercise test. If the resting ECG prior to the exercise test shows clinically significant abnormalities, the test will not be conducted. If abnormalities develop during the test, the test will be stopped. On both occasions, the participant will be referred to their Primary Care Physician for further evaluation. Before and after exercise activities are performed, the participant's that are type 2 diabetics will have a blood glucose checked using their home glucose monitor or glucose monitor at TRI. Blood glucose will be measured prior to and immediately following each exercise session for safety. If blood glucose is > 300mg/dl, study team will notify TRI provider immediately for review of glucose values, as well as medications. If the glucose values are consistently > 400mg/dl, participant will be instructed to follow up with their primary care physician. If blood glucose is < 100mg/dl, a snack will be given, and the participant will be allowed to exercise. Self-monitored blood glucose measurements should be checked anytime a patient has symptoms of hypoglycemia or hyperglycemia.

Aerobic fitness will be determined by measuring maximal O₂ consumption (VO_{2max}) during a stationary bicycle exercise test. Provider monitoring will follow The American

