and 180 degrees on each leg and gives a rating of P/D. Subject will perform three power tests on each leg and a 2 min rest between each increase in resistance. The subject will give a P/D rating after each trial. Before each test the tester will remind the subject to keep their back against the seat. If necessary other constant reminders will include – “Breathe normally,” “Look straight ahead,” or “Try to move your leg up to here (tester indicates end of movement).” The tester will also provide standard encouragement such as – “Move your leg as quickly as you can,” “Give me your best effort”. After both legs have been tested BP will be taken at conclusion of test and after 5-10 minutes of rest. If BP reading is normal, testing will continue. If it is above 160/100 mm Hg or has decreased by more than 15 mm Hg (top or bottom number) from the resting values, the subject will rest for 2 minutes and BP will be taken again. If BP has not normalized to below 160/100 mm Hg, further testing will be discontinued, and the subject will remain in the facility for at least ten more minutes while monitoring blood pressure. When BP finally normalizes, the subject will be sent home with the recommendation to contact their physician. The PI, [name], will also be notified.

Termination criteria for maximal power testing:

- A subject asks to discontinue testing.
- Equipment failure

Relative termination criteria:

- Subject reports >3 on the P/D scale (with explanation that the pain persists after the cessation of movement or if the subject reports >3 in any area besides the knee, upper or lower leg.

Before and after exercise activities are performed, the participant's blood glucose will be checked (type 2 diabetics only) using their home glucose monitor or glucose monitor at TRI. Blood glucose will be measured prior to and immediately following each exercise session for safety. If blood glucose is > 300 mg/dl, study team will notify TRI provider immediately for review of glucose values, as well as medications. If the glucose values are consistently > 400 mg/dl, participant will be instructed to follow up with their primary care physician. If blood glucose is < 100 mg/dl, a snack will be given, and the participant will be allowed to exercise. Self-monitored blood glucose measurements should be checked anytime a patient has symptoms of hypoglycemia or hyperglycemia.

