The following procedures, evaluations and/or assessments will be obtained daily during bed rest: 1) Medication/supplementation changes, 2) Vital signs consisting of body temperature, pulse rate (or heart rate), blood pressure, and respiratory rate will be monitored routinely (3 times daily). 3) Subjects will be interviewed to determine if any AEs/SAEs occurred in the last 24 hours. Medication to help mitigate reflux problems, constipation, and other issues associated with being supine will be available and administered per site standard of care or study physician discretion. All medications administered will be recorded.

Following 10 days of bed rest, the post bed rest recovery will consist of assisting the participant with ambulation and ensuring the participant is capable of showering, walking and dressing without assistance. The participant may stay an extra night at the study site for further recovery if it is deemed medically necessary by the study physician. A follow up phone call will be made that evening to ensure the subject is ambulatory and to inquire about any adverse events. The participant will return to the TRI on day 11 (+ 1 day) following discharge for additional post-bedrest assessments as listed below.

Before and after exercise activities are performed, the participant's blood glucose will be checked (type 2 diabetics only) using their home glucose monitor or glucose monitor at TRI. Blood glucose will be measured prior to and immediately following each exercise session for safety. If blood glucose is $> 300\text{mg/dl}$, study team will notify TRI provider immediately for review of glucose values, as well as medications. If the glucose values

are consistently $> 400\text{mg/dl}$, participant will be instructed to follow up with their primary care physician. If blood glucose is $< 100\text{mg/dl}$, a snack will be given, and the participant will be allowed to exercise. Self-monitored blood glucose measurements should be checked anytime a patient has symptoms of hypoglycemia or hyperglycemia.

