Capillary blood glucose will be measured four times a day for type 2 diabetics, before each meal and at bedtime. If two consecutive results of $> 240\text{mg/dl}$ are recorded, the study physician will review and change the patient's current treatment regimen (DPP-4 inhibitors, sulfonylureas and/or Metformin) to prevent further hyperglycemia. If two consecutive results of $> 270\text{mg/dl}$ are recorded, the study physician may initiate insulin therapy. Insulin therapy will continue until the participant reaches a target glucose range of 140–180 mg/dL (7.8–10.0 mmol/L). The participant's treatment regimen and diet will be reviewed and changed as necessary to prevent hypoglycemia ($< 70\text{ mg/dL}$), although this is not expected with medications like, DPP-4 inhibitors and/or Metformin.

The following table summarizes the schedule of assessment during Bed Rest.

Assessment	Bed Rest (Days)										
	1	2	3	4	5	6	7	8	9	10	11 (post BR)
Placement of Accelerometers	X	X	X	X	X	X	X	X	X	X	X
Adverse events	X	X	X	X	X	X	X	X	X	X	X
Medication/supplement history	X	X	X	X	X	X	X	X	X	X	
Eucaloric Diet - Adequate protein	X	X	X	X	X	X	X	X	X	X	
Vital signs	X	X	X	X	X	X	X	X	X	X	X
Passive Exercise⁴	X	X	X	X	X	X	X	X	X	X	
Incentive spirometer⁵	X	X	X	X	X	X	X	X	X	X	
Evaluate DVT risk	X	X	X	X	X	X	X	X	X	X	
Body Weight	X		X		X		X		X	X	
Metabolic Body Weight¹⁶											X
Glucose Clamp - 4Hr⁶											X
RMR¹⁰											X
24-Hour Urine											X
Blood draw (hemoglobin and hematocrit)⁷							X				X
Deuterated H₂O administration⁸										X	X
Fasting Muscle Biopsy/Blood draw¹											X
Fasting Adipose Biopsy² (optional)	X									X	
Anticoagulant Therapy		X	X	X	X	X	X	X	X		

DEXA³								X	
MR Assessments (ATPmax/IMCL/IMAT³)								X	
Orthostatic Hypotension Assessment¹¹								X	
VO₂max test									X
400m walk test									X
BiodeX/Strength testing								X	
SPPB								X	
Step Test								X	
Questionnaires⁹									X

¹Muscle Tissue Biopsy: For this study fasted is defined as consuming no food (except for water and allowed medications/dietary supplements) for at least 8 hours the before blood draw/muscle biopsy. Fasting status should be verified verbally with the subject. A venipuncture blood draw will also be taken prior to each muscle biopsy (Approximately 44ml on Day 10)). Blood will be processed, aliquoted and stored at -80C.

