Medication/Supplement Intake & Changes	X*	X*	X*	X ^{**}	X*	X*	X*	X ^{**}	X*	X*	X*	X*	X*	X*	X*	X ^{**}
Adverse Events	X*	X*	X*	X ^{**}	X*	X*	X*	X ^{**}	X*	X*	X*	X*	X*	X*	X*	X ^{**}
Metabolic Body Weight ¹⁶				X ^{**}				X ^{**}				X ^{**}		X ^{**}		X ^{**}
BIODEX/Strength Testing												X ^{**}				
Handgrip Strength												X ^{**}				
SPPB												X ^{**}				
Step Test												X ^{**}				
Questionnaires ²													X ^{**}			
DEXA				X ^{**}				X ^{**}				X ^{**}				X ^{**}
MR Assessments (ATPmax/IMCL/IMAT)				X ^{**}				X ^{**}				X ^{**}				X ^{**}

Accelerometer Handout															X*	X[^]
Accelerometer Collection						X*		X[^]								
VO _{2max} Test															X*[^]	
Cardio Exercise Program	X*	X*	X*		X*	X*	X*		X*	X*	X*		X*	X*	X*	
Strength Exercise Program	X*	X*	X*		X*	X*	X*		X*	X*	X*		X*	X*	X*	
Deuterated H ₂ O administration ⁸	X*[^]		X*[^]	X*[^]	X*[^]											
400m Walk Test															X*[^]	

* = only on this visit for exercise cohort

[^] = only on this visit for ambulatory cohort

Phase V – Optional Resistance Training.

Following Phase IV of the study, to expedite complete recovery, subjects may attend three resistance exercise training sessions per week over a four-week period, for a total of 12 visits. Resistance exercise training will include weight training of all major muscle groups. Subjects will perform three sets of eight repetitions at 70-80% of their 1 RM for each exercise, which will include upper body and lower body muscle groups. During all exercise sessions, subjects must be supervised by qualified personnel with the appropriate training to identify if the subject is under any type of distress. Study assessments will also be performed during the 4-week resistance training according to the table below:

Assessment	Resistance Training (Optional)											
	Week 1			Week 2			Week 3			Week 4		
	1	2	3	4	5	6	7	8	9	10	11	12
Vital Signs	X	X	X	X	X	X	X	X	X	X	X	X
Medication/supplement intake and changes	X	X	X	X	X	X	X	X	X	X	X	X
Adverse events	X	X	X	X	X	X	X	X	X	X	X	X
Metabolic Body Weight ¹⁶			X			X			X			X
Resistance Training ¹	X	X	X	X	X	X	X	X	X	X	X	X
BIODEX/Strength Testing	X											X
Handgrip Strength						X						X
SPPB						X						X
Step Test						X						X
Questionnaires ²						X						X
Accelerometer Collection		X										

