Therefore, we will mitigate risk of VTE in our high-risk participant population through prophylactic anticoagulation with low-molecular weight heparin given its safety profile and advantageous dosing frequency (qd vs. BID/TID for LDUH). Participants will receive enoxaparin 40mg subcutaneous injection, daily while immobile, with dose held only on the day of biopsies to minimize risk of bleeding or oozing intra- and post-procedurally. We will employ the daily passive exercise, throughout bed rest.

Every effort to prevent a study-related injury will be taken. If a DVT is suspected, the participant will be assessed by a provider, withdrawn from the study, and instructed to seek emergency treatment immediately. Sources: Prevention of VTE in Nonsurgical Patients - [https://journal.chestnet.org/article/S0012-3692\(12\)60124-X/fulltext](https://journal.chestnet.org/article/S0012-3692(12)60124-X/fulltext)

HIT - [https://journal.chestnet.org/article/S0012-3692\(15\)31496-3/pdf](https://journal.chestnet.org/article/S0012-3692(15)31496-3/pdf)

Pneumonia Prevention

Participants will also use an incentive spirometer 5-10 times (every 1-2 hours) daily to prevent pneumonia.

Glycemic management protocol. Hyperglycemia and hypoglycemia are risks for hospitalized patients with T2D and are associated with adverse health outcomes. To mitigate this risk patients with HA1C < 8.0% will be recruited. In addition, a glycemic management protocol will be administered for type 2 diabetics by the study physician. Capillary blood glucose will be measured four times a day, before each meal and at bedtime. If two consecutive results of > 240mg/dl are recorded, the study physician will review and change the patient's current treatment regimen (DPP-4 inhibitors, sulfonylureas and/or Metformin) to prevent further hyperglycemia. If two consecutive results of >270mg/dl are recorded, the study physician may initiate insulin therapy. Insulin therapy will continue until the participant reaches a target glucose range of 140–180 mg/dL (7.8–10.0 mmol/L). The participant's treatment regimen and diet will be reviewed and changed as necessary to prevent hypoglycemia (<70 mg/dL), although this is not expected with medications like, DPP-4 inhibitors and/or Metformin.

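### The pre-exercise glucose rule lets type 2 diabetic participants below 70 mg/dL exercise after a snack, with no recheck and no call to a provider

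*Protocol*

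**What the plan says.** The rule first appears under Screening Visit 2, note 8 (graded exercise testing). Type 2 diabetic participants have glucose checked before and straight after each exercise session, and for low values: "If blood glucose is < 100mg/dl, a snack will be given, and the participant will be allowed to exercise". The Biodex testing text in Phase II repeats it: "If blood glucose is < 100 mg/dl, a snack will be given, and the participant will be allowed to exercise". Phase III (Bed Rest) and Phase V (Optional Resistance Training) carry the same instruction.

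For high values the same paragraph escalates. Above 300 mg/dl the "study team will notify TRI provider immediately for review of glucose values, as well as medications", and values consistently above 400 mg/dl lead to a referral to the primary care physician.

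The protocol puts a number on hypoglycemia only in its bed-rest glycemic management text (Phase III, and again under Mitigation of Risks). There, treatment and diet are to be "changed as necessary to prevent hypoglycemia (<70 mg/dL"), with the remark "although this is not expected with medications like, DPP-4 inhibitors and/or Metformin". Inclusion criterion 2 nevertheless permits "DPP-4 inhibitors, Sulfonylureas and/or Metformin therapy".

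**The concern.** The condition is any value below 100 mg/dl, with one action attached. A participant at 95 and a participant at 60 are handled alike: a snack, then permission to exercise. Nothing requires staff to confirm that the snack has worked or to tell a clinician.

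The participants are 60 to 80 years old, and the VO2max test runs until the subject can no longer continue. Staff who follow the text exactly could start that test, a strength test or a training session in someone who is hypoglycemic by the protocol's own figure. This is a participant-safety issue in both arms. It does not bear on the statistical design.

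The gap is not one that a statistical analysis plan would fill. The protocol itself fixes the action.

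**Working it through.** The plan has no figure to reproduce here. The check is a reading of the rule, followed by a count of the occasions on which it applies.

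**1. What the rule covers.** Glucose below 100 mg/dl is made up of 70–99 and below 70. All four statements attach the same action to both ranges. None contains a floor, a reading between snack and start, or a low-side notification. The scheduled readings are one before and one after the session. An extra self-check is called for if symptoms occur, but no level for withholding exercise is attached to it.

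**2. How the protocol treats other abnormal findings around exercise.**
- Glucose above 300 mg/dl: provider notified at once (Screening Visit 2, note 8).
- Significantly abnormal resting ECG: the exercise test is not run (same note).
- Blood pressure above 160/100 mm Hg before strength testing: rest, recheck, and send home if still raised (Phase II, strength assessment).
- Glucose below 70 mg/dL: snack, then exercise permitted.

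The stopping criteria for the VO2max, strength and power tests contain no glucose item. Withhold-and-recheck rules are therefore already part of this protocol, and low glucose is left out of them.

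**3. Whether low readings are plausible.** Sulfonylureas are permitted, but the remark that hypoglycemia is not expected mentions only DPP-4 inhibitors and metformin. Insulin may be started during bed rest after two consecutive readings above 270 mg/dl, and strength and VO2max tests follow at the end of that phase. Screening Visit 2 combines a resting metabolic rate measured after an 8-hour fast with the VO2max test; the order and any meal between them are not stated. None of this gives a rate, and no rate is assumed.

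**4. How often the rule applies.** The unit is one scheduled visit, read from the assessment tables.
- VO2max tests: Screening Visit 2, post bed rest, recovery visit 15 = 3.
- Strength tests: pre-bed rest, post bed rest, recovery visit 12 = 3.
- CON: 3 + 3 = 6.
- EX training: visits 1–3, 5–7, 9–11 and 13–15 = 12. Visit 15 is already counted for its VO2max test, so EX is 6 + 12 − 1 = 17.
- Optional phase: 12 sessions in either arm. Its strength tests fall on sessions 1 and 12 and add nothing. CON is 6 + 12 = 18 and EX is 17 + 12 = 29.
- If step tests and 400 m walks also count as exercise, only Screening Visit 1 is added: CON 7 (19 with the optional phase), EX 18 (30).
- If the recovery strength test fell on a training visit instead of visit 12, EX would be 16 (28 with the optional phase).

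The rule is not restated under the Phase IV heading. Phase IV training is counted because the wording elsewhere covers each exercise session.

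**The case against.** The best counter-argument is that the rule is permissive and sits inside a supervised setting. Being allowed to exercise does not oblige staff to start. A certified exercise physiologist supervises both the recovery and the optional programs. Optional sessions must also be "supervised by qualified personnel with the appropriate training to identify if the subject is under any type of distress". A clinician attends exercise tests for at-risk subjects, the VO2max test follows ACSM guidance on provider monitoring, and the medical investigator can withdraw a participant for safety. All of that stands and lowers the risk. None of it sets a glucose level at which exercise is withheld, and checks triggered by symptoms help only when there are symptoms. What the ACSM guidance says about glucose is not in the document.

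The likelihood can also be questioned. Inclusion criterion 2a excludes participants on insulin, although the parent item lists basal insulins among the allowed agents, so the text is unclear. The remark about hypoglycemia not being expected gives examples and is not a closed list. During bed rest, glucose is measured four times a day and treatment is adjusted to avoid values below 70. These are fair points about frequency. They do not change what the rule permits when a low reading occurs.

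Finally, 70 mg/dL is a bed-rest management figure, not an exercise criterion. That is correct: the fault is a permission set too wide, not a contradiction between sections.

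**Conclusion.** The concern holds. For type 2 diabetic participants, the rule as written permits exercise at any glucose below 100 mg/dl after a snack, including values below 70, with no recheck and no notification. The fault amounts to one missing lower limit and the actions that should go with it. For 70–99 mg/dl the existing step is cautious and can stay.

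The rule applies on about 6 visits per type 2 diabetic participant in CON and 17 in EX, or 18 and 29 with the optional phase. These are occasions, not expected events, and they could shift by one or so depending on how the visit tables are read. The conclusion does not depend on them. Pre-diabetic participants fall outside the rule. Using 70 mg/dL as the withholding level is a choice made here, taken from the protocol's own definition of hypoglycemia. The change should be made on safety grounds; nothing in the sample size, power or analysis is affected.

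**What to change.** In all four places (Screening Visit 2 note 8, Phase II Biodex testing, Phase III Bed Rest, Phase V Optional Resistance Training), replace the low-glucose sentence with a two-step rule:

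- **70–99 mg/dl:** give a snack; exercise may proceed.
- **Below 70 mg/dL:** withhold exercise, treat, and notify the TRI provider. Start only after a repeat reading at or above 70 mg/dL; otherwise reschedule.

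The cost is one sentence changed in four repeated paragraphs, and an occasional delayed or rescheduled test or session.
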